#### **13.4.7.2.2. Treatment Compliance**

Treatment compliance is defined as the ratio of total study dose to the planned dose, in terms of percentage. Treatment compliance will be summarized descriptively.

Treatment compliance = the cumulative dose / the planned dose (4 tablets) \*100%.

The treatment compliance will be classified as 0, 25%, 50%, 75%, and 100%. This categorical data will be summarized with the frequency and percentage of subjects.

Non-compliance with dose regimen (example all four tablets taken as a single dose) will be captured based on investigator's review of subject diary.

### 13.4.8. Efficacy Analysis

The primary efficacy and secondary efficacy endpoints will be performed on the modified intent-to-treat set (mITT), and the intent-to-treat set (ITT). The mITT analyses will be considered primary; the ITT analyses will be considered supportive of the primary analyses on the mITT population. The denominator for all percentages will be the number of subjects in that treatment within the analysis set of interest, unless otherwise specified.

#### 13.4.8.1. Primary Endpoint

The primary efficacy endpoint is defined as the percentage of subjects with Clinical Success (at least 50% reduction from Baseline in the total composite VSS score with no additional antifungal therapy required based on investigator's judgment) at the test-of-cure (TOC) visit.

Clinical success will be assessed at the TOC Visit (Day 11) according to the following definitions:

- Clinical success: At least 50% reduction from Baseline in the total composite VSS score with no additional antifungal therapy required based on investigator's judgment prior to or at the TOC visit;
- Clinical failure: less than 50% reduction from baseline in the total composite VSS score or need for additional antifungal therapy. For the subject who early terminated before TOC visit and received additional vulvovaginal or systemic antifungal therapy or topical vaginal drug therapy for the treatment of vulvovaginal irritation/pruritus prior to or at the early termination visit, the subject is considered a clinical failure.

Signs of VVC will be defined as the presence of erythema, edema, or excoriation. Symptoms of VVC will be defined as itching, burning, or irritation.

Each vulvovaginal sign will be objectively scored based on severity as follows:

- 0 = none (complete absence of any signs or symptoms);
- 1 = mild (slight);
- 2 = moderate (definitely present);
- 3 = severe (marked, intense).

Each vulvovaginal symptom will be objectively scored based on severity as follows:

- 0 = none (I have no discomfort);
- 1 = mild (I have some discomfort, but it does not bother me much);
- 2 = moderate (I have discomfort, which is annoying, but not enough to affect what I am doing);
- 3 = severe (I have discomfort, which is annoying enough to affect what I am doing).

The composite score of the vulvovaginal signs and symptoms will be calculated according to the following rules and this scale has a total possible score of 18.

- If all items of the vulvovaginal signs and symptoms have been scored, the composite score is calculated as the sum of the individual scores of all 3 items of signs and 3 items of symptoms;
- If any sign or symptom is not done, the composite score will not be calculated and treated as a missing data except at FU visit;
- Subjects who are free of symptoms are not required per protocol to have a vaginal examination at FU visit, therefore signs are not considered missing. For subjects who do not present symptoms and have no sign rated at the FU visit, the composite score of the vulvovaginal signs and symptoms at the FU visit will be calculated as zero.

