#### **13.4.8.2. Secondary Efficacy Endpoints**

##### **13.4.8.2.1. Clinical Outcome – Clinical Cure**

A summary with the number and percentage of subjects with clinical cure at the TOC visit will be presented by Candida Species of the baseline yeast and overall. Clinical outcomes will be assessed at the TOC Visit (Day 11) according to the following definitions:

- Clinical cure: Complete resolution of signs and symptoms of vulvovaginal infection without need for further antifungal treatment and topical vaginal drug therapy for the treatment of vulvovaginal irritation/pruritus prior to or at the TOC visit. Specifically, for complete resolution, any sign or symptom should be absent (score = 0);
- Not clinical cure: No response to therapy or incomplete resolution of signs and symptoms or use of additional vulvovaginal or systemic antifungal therapy or topical vaginal drug

therapy for the treatment of vulvovaginal irritation/pruritus prior to or at the TOC visit. For the subject who early terminated before TOC visit and received additional vulvovaginal or systemic antifungal therapy or topical vaginal drug therapy for the treatment of vulvovaginal irritation/pruritus prior to or at the early termination visit, the subject is considered a not clinical cure.

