#### **13.4.8.2.4. Symptom Outcome**

A summary with the number and percentage of subjects with complete resolution of symptoms at the Follow-up (FUP) visit will be performed by Candida Species of the baseline yeast and overall. The subjects with missing Follow-Up data for the symptom outcome will be imputed as symptom persistence using the NRI method described in Section 13.4.4.4.

Symptom outcomes will be assessed at the FU Visit according to the following definitions:

- Symptom Resolution: All symptoms are absent (score = 0) without need for further antifungal treatment or topical vaginal drug therapy for the treatment of vulvovaginal irritation/pruritus prior to or at FU visit;
- Symptom Persistence: No response to therapy or incomplete resolution of symptoms or use of additional vulvovaginal or systemic antifungal therapy or topical vaginal drug therapy for the treatment of vulvovaginal irritation/pruritus prior to or at FU visit. For the subject who early terminated before the FU visit and received additional vulvovaginal or systemic antifungal therapy or topical vaginal drug therapy for the treatment of vulvovaginal irritation/pruritus prior to or at the early termination visit, the subject is considered a symptom persistence.

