#### **13.4.8.2.5. Clinical Improvement**

A summary with the number and percentage of subjects with clinical improvement (partial or complete resolution of signs and symptoms with total composite score no greater than 1 without need for further antifungal treatment and topical vaginal drug therapy for the treatment of vulvovaginal irritation/pruritus prior to or at TOC visit) at the TOC visit will be performed. For the subject who early terminated before the TOC visit and received additional vulvovaginal or systemic antifungal therapy or topical vaginal drug therapy for the treatment of vulvovaginal irritation/pruritus prior to or at the early termination visit, the subject is considered no clinical improvement. The subjects with missing TOC visit data for clinical improvement outcome will be imputed as no clinical improvement using the NRI method described in Section 13.4.4.4. The composite score will be calculated as the rules described in Section 13.4.8.1.

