#### **13.4.11. Changes in the Planned Analysis**

For the clinical failure definition, the texts “less than 50% reduction from baseline in the total composite VSS score” was used to replace “persistence and/or worsening of signs and symptoms” we have in the protocol.

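### In the sub-study, topical treatment for itch or irritation before TOC rules out Clinical Cure and Improvement for every woman, but rules out the primary Clinical Success only for early terminators

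*SAP*

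**What the plan says.** All references are to the sub-study, SCY-078-304S.

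- **Primary Clinical Success (SAP 13.4.8.1):** "at least 50% reduction from Baseline in the total composite VSS score with no additional antifungal therapy required", in the investigator's judgment. The general failure rule is the mirror image: "less than 50% reduction from baseline in the total composite VSS score or need for additional antifungal therapy". Neither mentions topical symptomatic treatment.
- **Early terminators (same section):** a further sentence does bring it in: "For the subject who early terminated before TOC visit and received additional vulvovaginal or systemic antifungal therapy or topical vaginal drug therapy" for irritation or pruritus, such a woman is a clinical failure.
- **Clinical Cure (SAP 13.4.8.2.1):** complete resolution "without need for further antifungal treatment and topical vaginal drug therapy for the treatment of vulvovaginal irritation/pruritus prior to or at the TOC visit".
- **Clinical Improvement (SAP 13.4.8.2.5):** a composite score of at most 1 "without need for further antifungal treatment and topical vaginal drug therapy for the treatment of vulvovaginal irritation/pruritus prior to or at TOC visit".
- **Protocol 21.3.14.5.1:** Success, Improvement and Cure all carry an antifungal condition only. The SAP's Success definition therefore agrees with the protocol, and the topical condition in Cure and Improvement was added by the SAP.
- **Changes list (SAP 13.4.11):** a single entry, beginning "For the clinical failure definition, the texts", which covers the 50% wording. The topical condition is not listed.

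**The concern.** Three outcomes measured at one visit on one scale follow two different medication rules. For women who attend TOC, symptomatic vaginal treatment is disqualifying for Cure and Improvement and ignored for the primary endpoint. Within the primary endpoint, the same treatment counts or does not count depending on whether the woman terminated early.

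The direction matters because the sub-study is open-label and single-group. Itching, burning and irritation are half of the VSS scale, are rated by the woman herself, and are what an antipruritic product treats. Relief from such a product cannot be separated from the drug effect by comparison with a control arm, so it is included in the ibrexafungerp success rate. The one planned sensitivity analysis of the primary endpoint (SAP 13.4.8.1.1) removes imputed outcomes and does not address this. A reader who compares the Success rate with the Cure and Improvement rates would also see a mixture of different score thresholds and different medication rules, with no notice that the second difference exists.

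**Working it through.** **1. The rules side by side, for a woman who used topical treatment for itch or irritation before TOC**

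| TOC outcome | Attends TOC | Terminates before TOC | Topical condition in protocol? |
|---|---|---|---|
| Clinical Success (primary) | not considered | failure | no |
| Clinical Improvement | not improved | not improved | no |
| Clinical Cure | not cured | not cured | no |

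The topical condition changes the result when the score alone would have qualified: a score of 0 for Cure, 0 or 1 for Improvement. A woman with a score of 0 at TOC after such treatment is a Success and, solely because of the treatment, neither cured nor improved.

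**2. Can symptom relief alone meet the primary criterion?**

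Inputs: six items scored 0 to 3 (SAP 13.4.8.1); entry score at least 3 (Protocol 21.3.7.1).

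- Symptom share: 3 items × 3 = 9 of 18 points.
- Baseline 3: success needs a score of at most 1, a fall of 2 points. Two symptom points and one sign point becoming zero and one is a Success with signs unchanged.
- Baseline 6: success needs at most 3, a fall of 3 points. Three symptom points and three sign points becoming zero and three is also a Success with signs unchanged.

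So it can, though only where symptoms carry at least half of the baseline score.

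**3. Which products fall in the gap?**

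Protocol 21.1.1 prohibits topical vaginal corticosteroids, and topical vaginal antifungals other than study drug or rescue. Sections 21.3.7.2 and 21.3.9.2 carry this into the sub-study. An additional topical antifungal is already a failure under the antifungal condition. What remains is other topical antipruritic products, plus prohibited corticosteroid use. No rule makes the latter a failure for a woman who attends TOC, and the sub-study has no per-protocol set (SAP 13.4.4.3).

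**4. Size**

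The plan's own figure first. For x successes in n, the Clopper-Pearson limits are the 2.5% quantile of Beta(x, n − x + 1) and the 97.5% quantile of Beta(x + 1, n − x). With x = 30 and n = 60 this gives 36.8% to 63.2%, as stated in SAP 13.4.4.1.

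The documents give no rate of topical use, so the number k of successes who used it is an assumption. Counting k of the 30 as failures:

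| k | Rate | 95% CI |
|---|---|---|
| 0 | 30/60 = 50.0% | 36.8% to 63.2% |
| 1 | 29/60 = 48.3% | 35.2% to 61.6% |
| 3 | 27/60 = 45.0% | 32.1% to 58.4% |
| 6 | 24/60 = 40.0% | 27.6% to 53.5% |
| 9 | 21/60 = 35.0% | 23.1% to 48.4% |

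Each woman moves the rate by 1/60 = 1.7 points, and by more if the mITT set, on which the primary analysis runs, is smaller than 60. As a measure of bias each line is an upper bound: some of the k women would have reached a 50% fall without the product.

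**The case against.** The strongest reply is that the primary endpoint is the one outcome of the three that follows the protocol. The unlisted change lies in Cure and Improvement, and redefining a protocol primary endpoint to match it would be the more intrusive repair. This stands, and it is why a sensitivity analysis is an acceptable alternative to changing the definition.

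Other points narrow the matter. The obvious topical anti-inflammatory products are prohibited. Women with persistent or worsening symptoms are strongly discouraged from treating themselves (Protocol 21.3.6.1). The investigator rates the signs, which are the other 9 of 18 points, so a score of 0 cannot come from symptom relief alone unless signs were already absent. The sub-study is exploratory and reports an estimate with an interval, without a test or a success threshold. Concomitant medications are tabulated and listed by subject (SAP 13.4.7.1.2), so users could be identified. All of this limits size and consequence; none of it reconciles the rules or supplies an analysis that does.

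Some stronger readings are tempting but unsupported:

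- **That topical treatment never affects the primary endpoint.** SAP 13.4.8.1 names it for early terminators.
- **That the early-terminator sentence is empty because missing-data rules fail those women anyway.** Protocol 21.3.7.3 asks for the TOC procedures at the early termination visit when consent is withdrawn on or before TOC. Non-responder imputation (SAP 13.4.4.4) applies only to missing response data. The sentence can therefore decide an outcome.
- **That Symptom Resolution shows the same conflict.** It too excludes such treatment ("All symptoms are absent (score = 0) without need for further antifungal treatment or topical vaginal drug therapy"), but it is assessed at follow-up, not at TOC, and is not a protocol endpoint (Protocol 21.3.5.2).

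**Conclusion.** The inconsistency is real. For women who attend TOC, topical vaginal treatment for itch or irritation is non-response for Clinical Cure and Clinical Improvement and is ignored for Clinical Success. The added condition in Cure and Improvement is not declared in SAP 13.4.11. These two statements rest on the text alone and hold whatever the frequency of use.

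The effect on the estimate can only be upward, but its size is unknown. A reader might infer that the reported rate will be inflated by 5 to 10 points. That would need 3 to 6 of 60 women to use a permitted or prohibited topical product, all of them to be successes, and none to have succeeded without it. The documents support none of these. What can be said is 1.7 points per reclassified woman at n = 60, as an upper bound on the bias, against a planned half-width of 63.2 − 50.0 = 13.2 points. Nor do the documents support saying that the SAP departed from the protocol's definition of Clinical Success. A change is worth making because it is cheap and protects an uncontrolled estimate.

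**What to change.** Choose one of two routes.

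1. In SAP 13.4.8.1, apply the topical-treatment condition to Clinical Success, and its converse to Clinical Failure, for all subjects regardless of early termination.
2. Keep the protocol definition of Clinical Success and add to SAP 13.4.8.1.1 a sensitivity analysis that counts topical vaginal treatment for irritation or pruritus, prior to or at TOC, as non-response.

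Under either route, list the departures from the protocol in SAP 13.4.11: the condition in Clinical Cure and Clinical Improvement and, if changed, in Clinical Success.

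The cost is a sentence or one extra table, plus the entries in 13.4.11. No new data are needed, because all medications from Baseline through TOC are already recorded (Protocol 21.3.9.1). The change concerns outcome classification only. The downside is that the rate reported under the stricter rule can stay the same or fall slightly; it cannot rise.

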#### **13.4.8.1.1. Primary Analysis**

The primary efficacy analysis will be performed on the mITT set at the TOC visit. The number and percentage of subjects with clinical success at the TOC visit will be presented. The 95% confidence interval of the clinical success rate will be calculated using the method of Clopper and Pearson. Missing data for clinical outcome will be imputed using the NRI method described in Section 13.4.4.4. Additional summarizations will be performed by Candida Species of the baseline yeast, but not subject to formal statistical analysis.

The same analysis employing the same methods as for the primary analysis will be performed for the ITT set to assess clinical success at TOC visit. Missing data for clinical outcome will be imputed using the NRI method described in Section 13.4.4.4.

A sensitivity analysis using the mITT set will be performed where subjects with the imputed clinical outcome using the NRI method at TOC visit will be removed from the analysis.

Summary of the number and percentage of subjects with continued clinical success at the Follow-up (FUP) visit, which defined as continued clinical success in subjects who achieved Clinical Success at the TOC visit, will be provided based on the ITT, and mITT sets.

#### **13.4.8.2. Secondary Efficacy Endpoints**

##### **13.4.8.2.1. Clinical Outcome – Clinical Cure**

A summary with the number and percentage of subjects with clinical cure at the TOC visit will be presented by Candida Species of the baseline yeast and overall. Clinical outcomes will be assessed at the TOC Visit (Day 11) according to the following definitions:

- Clinical cure: Complete resolution of signs and symptoms of vulvovaginal infection without need for further antifungal treatment and topical vaginal drug therapy for the treatment of vulvovaginal irritation/pruritus prior to or at the TOC visit. Specifically, for complete resolution, any sign or symptom should be absent (score = 0);
- Not clinical cure: No response to therapy or incomplete resolution of signs and symptoms or use of additional vulvovaginal or systemic antifungal therapy or topical vaginal drug

therapy for the treatment of vulvovaginal irritation/pruritus prior to or at the TOC visit. For the subject who early terminated before TOC visit and received additional vulvovaginal or systemic antifungal therapy or topical vaginal drug therapy for the treatment of vulvovaginal irritation/pruritus prior to or at the early termination visit, the subject is considered a not clinical cure.

#### **13.4.8.2.2. Mycological outcomes**

A summary with the number and percentage of subjects with mycological eradication (negative culture for growth of *Candida* species) at the TOC visit will be performed by *Candida* species of the baseline yeast and overall. The subjects with missing TOC visit data for the mycological outcome will be imputed as mycological persistence using the NRI method described in Section 13.4.4.4.

Mycological outcomes will be assessed at the specified visit according to the following definitions.

- **Mycological Eradication:** A subject with negative culture for *Candida* species without need for further antifungal treatment prior to the TOC visit. For subjects who are free of symptoms and have no vulvovaginal specimens obtained at the TOC visit, the subject will be considered as mycological eradication;
- **Mycological Persistence:** A subject with a positive culture for *Candida* species or use of additional vulvovaginal or systemic antifungal therapy prior to the TOC visit. For the subject who early terminated before TOC visit and received additional vulvovaginal or systemic antifungal therapy prior to the early termination visit, the subject is considered a mycological persistence.

The same analysis will be done for the percentage of subjects with mycological eradication (negative culture for growth of *Candida* species) at the FU visit. For subjects who are free of symptoms and have no vulvovaginal specimens obtained at the FU visit, the subject will be considered as mycological eradication at the FU visit.

The change of mycological outcomes will be summarized in shift tables comparing the testing results at TOC visit with those at FU visit.

The analyses for mycological outcome will only be conducted for the mITT set.

In addition, a summary table will be presented to include MIC range, mode, MIC50, and MIC90, based on the ITT and mITT sets by treatment group and geographical region (USA or Ex-USA) for the following MIC results from 2 different methods, CLSI and EUCAST, respectively:

- MIC results for SCY-078 and fluconazole (FLU) at 24 hours against *Candida* species isolates obtained at TOC visit;
- MIC results for SCY-078 and fluconazole (FLU) at 48 hours against *Candida* species isolates obtained at TOC visit.

Frequency cross-tabulations of mycological persistence at baseline versus mycological eradication at TOC visit will be presented by treatment group by candida species isolates obtained at baseline based on mITT set.

